Psychological well-being and person-specific levels of social interaction (i.e., changes in social engagement measured with the I-CONNECT Weekly Questionnaire administered weekly via telephone) will be monitored and controlled in the analyses along with other relevant variables, including APOE 4 status.

Video chats will be recorded and analyzed to determine longitudinal changes in speech patterns.

A. Analyses for Primary Outcomes

MoCA test scores (global cognitive function) are our primary outcome.

Secondary outcomes include: neuropsychological test results in the area of language-based executive function, measured by the T-Cog category fluency test (animals), and memory domains measured by

two T-Cog episodic memory tests (Craft Story Immediate and Delayed Recall). We will allocate a type I error rate of 0.05 for our primary outcome. The results will be cross-validated with NIH Toolbox cognitive batteries as exploratory analyses for those who had NIH Toolbox cognitive assessments. Potential mediation variables include the Psychological Well-Being portion of the NIH Toolbox. If Psychological Well-Being shows significant improvement in the experimental group compared to the control group over 6 months (in univariate analysis using $p < 0.05$), the measurement(s) will be examined as potential mediation factors in statistical models as secondary analyses. The Psychological Well-Being portion of the NIH Toolbox consists of 3 measurements: Positive Affect, Life Satisfaction, and Meaning and Purpose. The questionnaire and references for these scales are detailed in: <http://www.nihtoolbox.org/WhatAndWhy/Emotion/PsychologicalWell-Being/Pages/default.aspx>.

B. Sample Size Estimate

Our previous pilot study (based on a six-week intervention) showed Cohen's $d=0.53$ when comparing pre-post changes in language-based executive functions (Clinical Dementia Rating 0 and 0.5 groups combined) in the control and experimental arms. The sample size ($n=72$ completers for each group) in this trial provides 80% power to detect this difference at $\alpha=0.025$, using a two-tailed test (i.e., total type I error rate= 0.025), based on simulation results using non-pooled standard deviation (SD).

Two separate hypotheses are proposed. Stage I examines the efficacy of the high dose and Stage II examines the efficacy of the maintenance dose. Participants covered under the current protocol will be included into the high dose analysis

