Changes in primary and secondary outcomes between the control and experimental groups will be examined for the efficacy of high dose (month 0 – month 6, Stage I) and maintenance dose (month 6 – month 12, Stage II) using the Mixed-Effect Model Repeated Measure (MMRM) model under ITT. We will conduct per protocol analysis using those who completed at least 80% of targeted conversational sessions (experimental group) and the number of telephone check-ins (control group). The subjects recruited or in trial under the current remote trial protocol will be included where appropriate (i.e., high dose analysis).

Changes in primary and secondary outcomes between the control and experimental groups will be examined for the efficacy of high dose (month 0 – month 6, Stage I) and maintenance dose (month 6 – month 12, Stage II) using the Mixed-Effect Model Repeated Measure (MMRM) model under ITT. We will conduct per protocol analysis using those who completed at least 80% of targeted conversational sessions (experimental group) and the number of telephone check-ins (control group).

Changes in primary and secondary outcomes between the control and experimental groups will be examined for the efficacy of high dose (month 0 – month 6, Stage I) and maintenance dose (month 6 – month 12, Stage II) using the Mixed-Effect Model Repeated Measure (MMRM) model under ITT. We will conduct per protocol analysis using those who completed at least 80% of targeted conversational sessions (experimental group) and the number of telephone check-ins (control group).

[figure not shown]

Figure 1. Trial Dose Stages: Sample size for one group (MCI or normal cognition; both groups have the same planned sample size)

Changes in primary and secondary outcomes between the control and experimental groups will be examined for the efficacy of the high dose (Baseline-Month 6, Stage I) and the maintenance dose (Month 6-Month 12, Stage II) using the Mixed-Effect Model Repeated Measure (MMRM) model under intention-to-treat (ITT). We will conduct per-protocol analysis using those who completed at least 80% of the targeted conversational sessions (experimental group) and telephone check-ins (control group).

C. Analyses proposed for the New Aim 4

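### Does an alpha of 0.05 for MoCA conflict with a sample size built on 0.025, and does Stage II need its own error rule?

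*Combined protocol and SAP*

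**What the plan says.** All references are to the combined protocol and SAP.

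- **Primary alpha.** VIII.A names MoCA as the primary outcome and states: "We will allocate a type I error rate of 0.05 for our primary outcome". The same section places the powered domain lower: "Secondary outcomes include: neuropsychological test results in the area of language-based executive function".
- **Sample size.** VIII.B takes d = 0.53 from a six-week pilot, obtained "when comparing pre-post changes in language-based executive functions". It says that 72 completers per group "in this trial provides 80% power to detect this difference at" an alpha of 0.025, "using a two-tailed test (i.e., total type I error rate= 0.025").
- **Stages.** VIII.B continues: "Two separate hypotheses are proposed. Stage I examines the efficacy of the high dose and Stage II examines the efficacy of the maintenance dose". Primary and secondary outcomes are analysed in both stages, including "the maintenance dose (Month 6-Month 12, Stage II) using the Mixed-Effect Model Repeated Measure (MMRM) model under intention-to-treat (ITT"). On the remote participants it says: "The subjects recruited or in trial under the current remote trial protocol will be included where appropriate (i.e., high dose analysis").
- **Scope.** Aim 1 in section II sets the efficacy question as change from baseline to six months and bases the primary MoCA analysis on the pre-pandemic cohort alone. The opening of section VIII leaves the analysis approach to the main I-CONNECT protocol, which is not among the documents supplied. Figure 1 in VIII.B, on dose stages and sample size, is not reproduced.

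**The concern.** Two adjacent subsections give two type I error rates, and VIII.B calls its 0.025 the total. A reader could infer that 0.05 was meant to be split across two hypotheses, and then ask whether a month 6 MoCA result with p between 0.025 and 0.05 counts as a success.

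The power statement adds to the doubt. It concerns a secondary domain, so a quick reader might take its 80% as power for MoCA.

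Stage II raises a further question. MoCA is to be examined for efficacy in both periods, with no test order, alpha split or exploratory label. If each stage were a confirmatory test at 0.05, the chance of at least one false positive on MoCA would exceed 0.05. Investigators are not blinded to allocation (IV.C.3), so a rule left open until the data are seen would be a real weakness.

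**Working it through.** **1. Reproduce the plan's figure.** Inputs from VIII.B: n = 72 completers per arm, d = 0.53, two-sided alpha 0.025. Allocation is 1:1 (section IV). No SD is given, so the calculation uses standardized units.

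- Noncentrality: d × √(n/2) = 0.53 × √36 = 3.18, with 2 × 72 − 2 = 142 degrees of freedom.
- At two-sided 0.025 the critical t is 2.265 and power is **81.9%**.
- At two-sided 0.05 the critical t is 1.977 and power is **88.5%**.
- The smallest n per arm for 80% power is 69 at 0.025 (80.0%) and 57 at 0.05 (80.1%).
- A simulation with an unpooled-variance t-test (100,000 runs), the form of SD that VIII.B names, gives 81.9% and 88.5%.

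The stated 80% therefore fits two-sided 0.025, with a margin of three per arm. It was not computed at 0.05, so the 0.025 is not a typing slip. These figures use a two-sample comparison, not the MMRM.

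**2. Which alpha governs MoCA?** VIII.A ties 0.05 to the primary outcome by name. VIII.B ties 0.025 to a specific difference, the pilot effect in executive function. A planning alpha for one outcome sets no success threshold for another. A month 6 MoCA p-value of 0.04 meets the only alpha allocated to MoCA.

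**3. How large would the disputed zone be?** The smallest observed standardized difference that is significant is the critical t times √(2/n). The chance of landing in the zone is power at 0.05 minus power at 0.025.

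| Per arm | Zone of observed d | Chance, d = 0 | Chance, d = 0.35 | Chance, d = 0.53 |
|---|---|---|---|---|
| 72 | 0.33 to 0.38 | 2.5% | 11.4% | 6.6% |
| 52 | 0.39 to 0.45 | 2.5% | 10.8% | 9.8% |

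Neither row describes the actual MoCA test. That analysis is limited to the pre-pandemic cohort, whose size is not stated, and no MoCA effect size is given. The 52 is an illustration: it assumes that the 72 includes the roughly 40 remote participants, split evenly (72 − 40/2 = 52). Both rows matter only if 0.025 competes with 0.05 for MoCA, and step 2 shows that it does not.

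**4. Stage II error rate.** Two tests, each at two-sided 0.05, both null hypotheses true:

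- Independent: 1 − 0.95² = 0.0975.
- Correlation −0.5: 0.0907. Correlation −0.7: 0.0835. The correlations are assumed.
- Two tests at 0.025 each, independent: 1 − 0.975² = 0.0494.
- Stage I alone carrying the claim, or Stage II tested only after a significant Stage I: 0.05.

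The last line fits Aim 1, which asks only about baseline to six months. The figures above 0.05 require both stages to be confirmatory at 0.05, and no sentence says so. The 0.0494 shows that 0.025 would suit an equal split over two hypotheses. That is a possible origin for it, but the text does not confirm it.

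**The case for a change.** The strongest contrary case is that the alpha and power figures are restated in this document and ought to agree here; deferring to another protocol does not reconcile two numbers a few lines apart. The Stage II efficacy analysis is described several times, so its status belongs here too. A few dated sentences would cost little, and with unblinded investigators they would have some value.

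Part of this stands. The text does not explain the 0.025, gives no power for MoCA and does not label Stage II. A reader must not carry the 80% over to the MoCA test: both the outcome and the analysed cohort differ.

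The remedies that suggest themselves gain little. Restating executive-function power as 88.5% at 0.05 would apply the primary outcome's alpha to a secondary outcome, replace a conservative basis with a more favourable one, and correct no wrong figure. Gating Stage II behind Stage I would control error over both tests, but would bar any Stage II claim if Stage I failed. For what the document calls separate hypotheses about two doses that is a trade-off, and reporting Stage II as secondary or exploratory would serve equally well. Remote participants, in the study for about seven months (section IV), do not enter Stage II at all.

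**Conclusion.** The concern is accurate about the wording but does not call for a change. Followed as written, the plan gives a sound month 6 MoCA test at 0.05. The sample size claim is correct and slightly conservative for the outcome it names: 81.9% against 80%, with 72 planned and 69 needed.

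The gap is explanatory, and analysts can fill it sensibly: read 0.025 as the planning value for executive function, treat month 6 as the confirmatory time point, and report Stage II as supporting evidence unless the main protocol says otherwise. Family-wise error of up to 0.0975 is a conditional figure, not a property of the plan.

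This conclusion rests on two readings. One is that the alpha in VIII.A applies to the month 6 comparison in Aim 1, as a two-sided test; VIII.A does not state the sidedness. The other is that nothing in the unsupplied main protocol or the missing Figure 1 makes both stages confirmatory at 0.05. The lack of a power basis for MoCA is a separate matter, and choosing between 0.025 and 0.05 would not resolve it.

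### The p<0.05 screen on the well-being scales biases upward, on average, any indirect effect reported after it; the bias matters if the true effect on well-being is modest.

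*Combined protocol and SAP*

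**What the plan says.** The rule is in Section VIII.A (Analyses for Primary Outcomes). It introduces the candidates with "Potential mediation variables include the Psychological Well-Being portion of the NIH Toolbox" and then sets the condition: "If Psychological Well-Being shows significant improvement in the experimental group compared to the control group over 6 months (in univariate analysis" at p<0.05). For scales that meet it, "the measurement(s) will be examined as potential mediation factors in statistical models as secondary analyses". The scales are named: "The Psychological Well-Being portion of the NIH Toolbox consists of 3 measurements: Positive Affect, Life Satisfaction, and Meaning and Purpose".

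The section names no estimator for a mediated effect, no interval method, no allowance for the screening step and no multiplicity rule across the three scales. Section VIII refers the general analysis approach to the main I-CONNECT protocol, which is not among the documents reviewed. Nothing in the present document removes or corrects the screen.

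Section VI.C.3 and the Schedule of Events (XI.B) place the emotional-domain questionnaires at Baseline and Month 6 without restricting them to one arm, so the mediator data are collected whether or not the screen is passed.

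**The concern.** An indirect effect is usually estimated as a product: the effect of treatment on the mediator (path a) times the slope of the outcome on the mediator given treatment (slope b). The screen is a significance test of path a. If a scale is analysed only when its estimated a is large enough to be significant, and the same data then supply that estimate, the reported values of a are a selected upper part of their distribution. The product a×b inherits the inflation whenever b is not zero.

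The same rule has a second effect. When the true effect on well-being is modest, the screen often fails and the scale is not examined as a mediator at all. A reader then has no interval to show whether mediation was absent or merely imprecisely estimated.

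What is at stake is the interpretation of a secondary analysis of mechanism, not the efficacy conclusion.

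**Working it through.** **Inputs from the plan.** Completers per group: 72 (VIII.B), read here as per arm. Allocation 1:1 (IV). Screen: univariate p<0.05 for improvement (VIII.A), taken as two-sided with the effect in the favourable direction. Number of scales: 3 (VIII.A).

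**Assumptions not in the plan.** True standardised effects on well-being of d = 0.2 to 0.53. For the product, slope b = 0.3 and direct effect 0.2.

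**The plan's own figure.** VIII.B states 80% power for d = 0.53 with 72 per group at two-sided alpha 0.025, from simulation with non-pooled SD. A Welch-test simulation (100,000 runs) gives 81.9%, as does the noncentral t distribution. The stated figure is reproduced, which supports reading 72 as per arm. That d = 0.53 refers to language-based executive function, not well-being.

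**Step 1: threshold.** SE(d) ≈ √(2/72) = 0.167. A scale passes if its estimate exceeds 1.96 × 0.1667 = 0.327.

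**Step 2: pass probability and mean estimate given passing.** With z = (0.327 − d)/0.167, P(pass) = 1 − Φ(z) and E[estimate | pass] = d + SE × φ(z)/(1 − Φ(z)).

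At d = 0.2: z = 0.760, φ(z) = 0.299, P(pass) = 0.224. The mean is 0.2 + 0.1667 × 0.299/0.224 = 0.423, and 0.423/0.2 = 2.1.

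| True d | P(pass) | Mean estimate given passing | Inflation |
|---|---|---|---|
| 0.2 | 22% | 0.423 | 2.1× |
| 0.3 | 44% | 0.450 | 1.5× |
| 0.4 | 67% | 0.490 | 1.2× |
| 0.53 | 89% | 0.566 | 1.07× |

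The scale goes unexamined 78%, 56%, 33% and 11% of the time. At d = 0.8 the inflation is nil (1.00×).

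**Step 3: does this carry to the indirect effect?** The product a×b was simulated (20,000 trials per row, b = 0.3, direct effect 0.2):

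| True d | True a×b | Mean, no screen | Mean, passing trials |
|---|---|---|---|
| 0.2 | 0.060 | 0.060 | 0.126 |
| 0.3 | 0.090 | 0.090 | 0.135 |
| 0.4 | 0.120 | 0.120 | 0.147 |
| 0.53 | 0.159 | 0.159 | 0.170 |

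Without the screen the mean equals the truth. With it, the inflation factors match Step 2, because the estimate of b is not disturbed (mean 0.30). With a true d of zero, a passing scale shows a mean indirect effect of 0.117 instead of 0.

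**Step 4: proportion mediated.** As a ratio of mean indirect to mean total effect, at d = 0.2 the truth is 0.060/(0.2 + 0.060) = 0.23, and after the screen 0.126/(0.2 + 0.126) = 0.39, or 1.7-fold. At d = 0.3 it goes from 0.090/0.290 = 0.31 to 0.135/0.335 = 0.40, or 1.3-fold. At d = 0.53 the factor is 1.04. It is inflated less than a×b because a chance-high mediator effect also raises the total.

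**Step 5: three null scales.** Each passes in the direction of improvement with probability 0.025. If they are independent, P(at least one) = 1 − 0.975³ = 7.3%. With an assumed common correlation of 0.5 or 0.7 it is 6.3% or 5.5%.

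**Sensitivity to the meaning of group.** The Figure 1 caption uses the word for cognitive-status groups. At d = 0.3 the inflation would be 2.0× with 36 per arm and 1.18× with 144.

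**The case against.** The best defence is that testing the treatment-to-mediator path first is a recognisable stepwise approach to mediation, that the rule is fixed in advance, and that the analysis is labelled secondary. All of that is true. But stating a selection rule in advance does not make the estimates that survive it unbiased. A confidence interval for the indirect effect already shows when path a is weak, so the screen adds no protection that the interval lacks.

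The plan also does not promise an indirect-effect estimate; it says only that passing scales will be examined in models. The bias therefore applies to an indirect effect if one is reported. This stands as a limit on the point.

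Nor is well-being looked at only behind the screen. Aim 2 plans an unconditional look at change in the Emotion Battery total. Section VIII says psychological well-being will be controlled in the analyses. The list of potential mediators in VIII.A is open-ended. None of these estimates mediation through the three named scales, so the criticism holds for those scales and no further. The wording also leaves some doubt whether the screen applies to each scale or to the domain; the optional plural in "the measurement(s) will be examined as potential mediation factors in statistical models as secondary analyses" points to each scale.

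A reader might infer more: that the trial must report either no mediation or an exaggerated share mediated, and so could not say whether well-being carries the effect. The documents do not support that. They promise no share mediated, the share is inflated less than the path, and the bias is an average over passing trials that becomes small as the true effect grows. Nor is 7% a false-mediation rate: it assumes independent scales, and a scale that passes must still be associated with the outcome.

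**Conclusion.** The point holds in a limited form. Any indirect effect reported for a well-being scale after this screen is biased upward on average over trials that pass, as long as the mediator-outcome slope is not zero, and modest true mediators are often left unexamined. It follows from a rule the plan states, not from a missing detail.

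The size cannot be fixed from the documents, which give no expected effect on well-being. Over the assumed range it runs from about double at d = 0.2 to about 7% at d = 0.53, and the pilot's d = 0.53 for a cognitive outcome gives no assurance that well-being sits at the favourable end. These figures rest on 72 completers per arm; the proportion-mediated figures also need the assumed slope and direct effect.

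The primary MoCA result, its 0.05 type I error and the secondary cognitive outcomes are untouched. This is a cheap improvement, not a threat to the trial's main conclusion.

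**What to change.** In VIII.A, remove the p<0.05 condition. Estimate the indirect effect for each of Positive Affect, Life Satisfaction, and Meaning and Purpose, whatever its univariate result. Give bootstrap confidence intervals and report all three, labelled exploratory. Adding bootstrap intervals while keeping the screen would not cure the problem, because the selection would remain.

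The cost is a few extra models on questionnaires this protocol already schedules at Baseline and Month 6. The downside is more null or imprecise mediation results to report.

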Aim 2: Exploratory analysis: To examine the efficacy of our intervention on emotional well-being, resting-state fMRI (5 large networks), and functional measures.

Changes from baseline to Month 6 in the psychological well-being assessed by the NIH Toolbox Emotion Battery (emotion items total score), resting-state functional MRI (5 large networks) and IADL using OTDL-R (the Revised Observed Tasks of Daily Living) will be examined.

Aim 3: Exploratory analysis: To examine whether the intervention could lead to changes in speech and language characteristics over time.

There is a need to develop ecologically valid outcome measures sensitive to trial effects. Previous studies from our group showed that speech and language characteristics (e.g., word counts, sentence complexity) differentiated participants with MCI from those with intact cognition cross-sectionally.

We will record and analyze subjects' conversational sessions during the trial to examine whether algorithms used for the cross-sectional analyses can detect changes in speech and language characteristics induced by the intervention over time. We hypothesize that speech and language characteristics among participants with MCI will increasingly resemble those observed among the subjects with intact cognition over time.

Aim 4: Exploratory Analysis: Early identification of MCI using I-CONNECT and CART data (IRB# 17123) (secondary data analyses).

We hypothesize that the integration of language markers from all available video chat audio recordings can improve MCI screening accuracy. Specifically, we will:

1. Identify MCI by applying machine learning methods to I-CONNECT language markers. We will develop predictive models characterizing MCI using natural language processing (NLP) and machine learning (ML) algorithms to extract linguistic variables from the transcribed dialogues and acoustic variables. We will then link the variables with the cognitive status (MCI/normal cognition) and use the language markers to develop ML algorithms that fuse the information from the two modalities (linguistic and audio) to carry out early identification of MCI.
2. **Identify MCI by using the behavioral markers collected in the CART (IRB 17123). The similar machine learning methods will be applied to this data set which includes highly frequently in-home monitored data such as computer usage, walking speed and variability, time out of the house. .**

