3. Fuse CART digital biomarker data and I-CONNECT language markers to further boost the model screening performance.

III. Background

In recognition of the COVID-19 public health threat, Oregon Health & Science University suspended all in-person, *nonessential research on human subjects* on March 15th, 2020. The governor of Oregon went on to issue a stay-at-home order shortly thereafter. These restrictions lifted enough to permit remote trial

conduct and contactless materials delivery to subjects by June 8th. However, given the ongoing pandemic and uncertainty around possibly future COVID-19 restrictions, as well as the high-risk nature of our subject population (adults age 75 and older), it became necessary to adapt the protocol for remote conduct.

IV. Study Design

This study is a two-arm randomized controlled trial.

Participants will be randomized in a 1:1 ratio to the experimental or control conditions balancing the following factors:

- Cognitive status (healthy normal vs. MCI)
- Age (age 75-79 vs. age 80-84 vs. over 85+)
- Education (high school completion vs. below high school education)
- Sex (male vs. female)
- Mean Montreal Cognitive Assessment (MoCA)

Subjects will complete in-home assessments at the 6-month time point. All subjects will receive a follow-up telephone call approximately one month after the intervention period concludes. Subject participation in the study will last approximately seven months including the screening and follow-up period. In total, there are approximately four scheduled assessment calls (if assessment time points are split into multiple calls), plus additional technology troubleshooting calls, depending on group allocation.

A. Intervention Group

Half of participants will be randomized to the experimental group, the study intervention group. These subjects will engage in video chat conversations with study staff using an online video communication platform. Each video chat session will be 30 minutes long. Subjects will also receive a weekly telephone call, lasting approximately 10-15 minutes, to assess health and social activities.

The intervention period will last 24 weeks. Subjects in the intervention group will receive four chats per week (a high dose of the video chat intervention) for 24 weeks. The video chat frequency will then taper to a decreased dose of two chats per week during weeks 25 and 26 of the follow-up period.

B. Control Group

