Randomization to the control group or intervention group will occur prior to the Baseline visit, but subjects should not be notified of their group assignment until after the Baseline visit to help prevent the subjects from inadvertently unblinding the assessment staff.

If subjects are randomized but then withdraw and do not complete the Baseline visit, they will be removed from the randomization program to ensure study arms remain balanced. These subjects will be classified as drop-outs prior to randomization, as they are not informed of their group assignment.

If cohabitating subjects enroll in the trial, forced randomized will be used to assign the subjects to the

same study condition.

H. Intervention Period

The 24-week intervention period will begin once the Baseline procedures are complete. The intervention period will always start on a Monday.

For all subjects, Week 1 of the intervention period will start no more than two Mondays after the last Baseline-period procedure (the Baseline assessment or the technology installation, as applicable).

If a subject's Week 1 Day 1 is delayed more than 6 months from the date of their Screening visit, the subject will be rescreened. See section VI. E. Eligibility for rescreening details. Screening and Baseline data will be recollected.

1. Video Chat Intervention *Week 1 through Week 24*

The study intervention consists of structured 30-minute video chats between participants and study staff. Video chats will be conducted remotely using an online audio and video communication platform and a video chat device installed in the subject's home. The video chats will be audio and video recorded.

Novel conversation stimuli are provided for each chat, focusing on a theme with three possible topics and corresponding photos, to be visually presented to the participant during the chat via the video chat device. Stimuli include questions targeting three domains of cognition: episodic memory, semantic memory, and executive function. Stimuli will be used to initiate each chat, however subjects may direct the conversation as they find interesting or engaging. Study staff will attempt to maintain a neutral or positive chat tone.

The full chat intervention will last for 24 weeks. Chats will occur four days per week.

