The analysis of the New Aim 4 investigated the effectiveness of language markers from conversation in detecting early MCI subjects, where the key hypotheses are that 1) data-driven language and acoustic markers are predictive of early MCI subjects, 2) behavior markers from CART study are predictive of early MCI subjects, and 3) fuse both data to further improve the ability of identifying MCI

Aim 4 (1): To validate the first hypothesis of effectiveness of language and acoustic markers, we will first pre-process the data and extract acoustic markers and linguistic markers. We will apply automatic speech recognition (ASR) models to convert the collected conversations to machine-readable text in computer. We will then use OpenSMILE to extract Mel-frequency cepstral coefficients (MFCC) from the raw acoustic recordings as acoustic features in our analysis. For each recording, we will compute various types of feature representations (hand-crafted, statistical, and deep) from the MFCC features and compare them using their quality as evaluated in downstream analysis. Next, we will investigate one conventional bag-of-words feature representation using linguistic Inquiry and Word Count (LIWC) and deep-learning based embeddings.

We will first investigate the correlation of the two linguistic feature representations and their effect on classification performance on MCI detection. We will then compare the inclusion of MFCC features and investigate the effects on the classification performance. For classification models, we will use the de-identified interview data from I-CONNECT to assess the performance of the multi-modal predictive models using standard performance measures such as the area under the ROC curve (AUC), sensitivity, specificity, etc. We will randomly divide the data into three sets (80% for training, 10% for validation, and 10% for test), and perform 10-fold cross-validation to minimize the variability in the training set. Stochastic gradient descent will be used for training deep learning models, and first-order gradient descent will be used for non-deep learners. To compare the performance of different algorithms, we will compute the p-value to measure the significance of improvements over the 10-fold evaluations.

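### Aim 4 does not say whether recordings or participants are divided at random, so one speaker may sit in both training and test data and inflate the reported MCI accuracy

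*Combined protocol and SAP*

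**What the plan says.** Aim 4 (Section II) rests on the hypothesis that "the integration of language markers from all available video chat audio recordings can improve MCI screening accuracy". The extracted variables are to be used to "link the variables with the cognitive status (MCI/normal cognition"), which is an attribute of the person and not of a chat.

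Section VIII.C, Aim 4 (1), sets out the method:

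- Features: "For each recording, we will compute various types of feature representations (hand-crafted, statistical, and deep) from the MFCC features".
- Division: "We will randomly divide the data into three sets (80% for training, 10% for validation, and 10% for test").
- Resampling: "perform 10-fold cross-validation to minimize the variability in the training set".
- Comparison of algorithms: "we will compute the p-value to measure the significance of improvements over the 10-fold evaluations".

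The section does not name the unit that is divided or folded. No other section says that one participant's recordings must stay together.

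On volume, Section IV.A states: "Subjects in the intervention group will receive four chats per week (a high dose of the video chat intervention) for 24 weeks". It then tapers to two chats a week in weeks 25 and 26. Footnote j of the Schedule of Events limits video chats to the intervention group. Section VII.C acknowledges that the recordings carry voiceprints.

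Aim 4 (2) reuses the same training and testing scheme for the CART sensor data. Aim 4 (3) works with patient-level vectors and carries over the evaluation metrics without restating the split.

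**The concern.** A screening tool is applied to people it has never met, so its accuracy has to be measured on people who were absent from training. If one person's recordings are scattered over the training, validation and test sets, a classifier can do well by recognising the voice and returning the label already seen for that voice. MFCC features are computed from the raw sound and can carry speaker identity.

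Three results are exposed. The headline AUC, sensitivity and specificity could be too high. The planned comparison with and without MFCC could favour MFCC because it helps to identify speakers. The p-values over folds would inherit both problems, and choosing a model on a validation set with the same overlap would reward the same behaviour.

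**Working it through.** The plan gives no AUC, sample size or power for Aim 4, so there is no stated figure to reproduce. Two checks apply.

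**Inputs from the protocol.** Planned chats per intervention participant: 4 x 24 = 96, plus 2 x 2 = 4 in the taper, total 100 (Section IV.A). Controls contribute none (Schedule of Events, footnote j). Set probabilities are 0.8, 0.1 and 0.1 (Section VIII.C).

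**Check 1: overlap if recordings are divided.** Let a speaker have k recordings, each assigned independently.

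- P(speaker of a test recording is also in training) = 1 - 0.2^(k-1).
- P(all of a speaker's recordings fall in one set) = 0.8^k + 2 x 0.1^k.

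| k | Speaker also in training | All in one set |
|---|---|---|
| 2 | 1 - 0.2 = 0.80 | 0.64 + 0.02 = 0.66 |
| 5 | 1 - 0.0016 = 0.998 | 0.33 |
| 10 | above 0.999 | 0.11 |
| 96 | 1 to rounding | about 5 x 10^-10 |
| 100 | 1 to rounding | about 2 x 10^-10 |

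Ten folds used as eight for training, one for validation and one for test give the same overlap formula. With nine training folds, 0.2 becomes 0.1 and overlap is higher still. If participants are divided, overlap is zero by construction.

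**Check 2: simulated AUC with no MCI signal.** These assumptions are not from the documents: 40 or 72 speakers, half labelled MCI; 48 recordings each; 39 Gaussian features unrelated to the label; within-speaker correlation 0.1, 0.3 or 0.5; one 80/10/10 split; a ridge linear classifier and a 5-nearest-neighbour classifier; 40 replicates. Only the 72 has a link to the protocol, as the completers per group in Section VIII.B. Mean test AUC, by recording / by participant:

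| Speakers | Correlation | Linear | Nearest neighbour |
|---|---|---|---|
| 40 | 0.1 | 0.65 / 0.51 | 0.57 / 0.50 |
| 40 | 0.3 | 0.77 / 0.54 | 0.92 / 0.51 |
| 40 | 0.5 | 0.85 / 0.55 | 1.00 / 0.49 |
| 72 | 0.1 | 0.62 / 0.51 | 0.55 / 0.50 |
| 72 | 0.3 | 0.70 / 0.50 | 0.88 / 0.49 |
| 72 | 0.5 | 0.77 / 0.51 | 1.00 / 0.50 |

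The participant-level values of 0.49 to 0.55 are chance within simulation error. With 40 speakers the test set held two people per class, so the null standard deviation of one AUC is at most about sqrt(5/48) = 0.32, and 0.32/sqrt(40) = 0.05 for the mean.

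A second set-up used 72 speakers, 40 recordings each, 13 features, no signal and 10-fold cross-validation, with between-speaker variance shares of 0.20, 0.33 and 0.50. A 15-nearest-neighbour classifier gave 0.57, 0.71 and 0.87 by recording and about 0.47 by speaker. A linear classifier gave 0.60, 0.63 and 0.66 by recording. The direction is the same throughout, but the size depends heavily on the classifier.

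**The case against.** The strongest reply is that the plan never says recordings are divided. A reader might infer that it does, and that the reported accuracy will therefore be inflated. The documents do not support that. The per-recording wording governs how MFCC representations are built. The later split sentence refers only to data, with no unit. The hypotheses in Section VIII.C concern identifying subjects with MCI, the same scheme is applied to CART data where there are no recordings, and Aim 4 (3) classifies patient vectors. A participant-level split fits all of this. What stands is that a compatible reading is not a rule: two analysts who both follow Section VIII.C could split differently and get very different AUCs from the same data.

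A reader might also take an AUC such as 0.87 as the expected bias. It is not. It comes from one nearest-neighbour classifier that the plan does not name and from assumed variance shares. A linear model in the same set-up gave 0.66.

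Three further limits are fair:

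- The count of 100 chats applies to intervention participants under this remote protocol, which anticipates about 40 subjects. Chat counts for the maintenance stage of the wider trial are not given here.
- Diagnosis is repeated at Month 6, and the plan does not say which diagnosis supplies the label, so a constant label per person is likely but not stated.
- Voice recognition cannot affect the CART data. There the parallel risk is several time windows from one person falling in different sets.

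Keeping cohabiting pairs in one fold does not follow from this argument: they have different voices and may have different labels, and Section VI.G only places them in the same arm.

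**Conclusion.** The concern holds as an unspecified split unit with a real consequence. The plan permits a recording-level division, and under it overlap of speakers between training and test is practically certain at the planned number of chats. Performance would then partly reflect who is speaking. With no signal at all, simulated AUC ranged from about 0.55 to 1.00 by recording against about 0.5 by participant. That range depends on the assumed classifier, within-speaker correlation and numbers of speakers and recordings. It does not estimate this trial's bias, which would be zero from this source if participants are divided.

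This should be settled before the Aim 4 models are fitted. Aim 4 is labelled exploratory and is a secondary data analysis, so randomisation and the primary MoCA analysis are not touched.

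**What to change.** In Section VIII.C, make the participant the unit of random division and of the folds. Suggested wording: *Participants will be allocated at random to training, validation and test sets, and to folds; all recordings of a participant, and in Aim 4 (2) all CART time windows of a participant, will be kept in one set or fold.* State that the same rule holds for Aim 4 (3).

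Add that feature choice and tuning use training and validation participants only. Report AUC, sensitivity and specificity at participant level, with an interval that reflects the number of participants and not the number of recordings. State which diagnosis, Screening or Month 6, supplies the label.

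The cost is a few sentences and a grouped split in the code. The reported accuracy may be lower, and it will be less precise. If 72 speakers contribute (an assumption taken from the 72 completers per group), one 10% test set holds about 0.10 x 72 = 7 people, so the interval will be wide. If the sponsor already intended a participant-level split, the change only records that.
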